### **Study Population**

It is estimated that up to approximately 30 patients will participate in the study at the Sheppard Pratt site with 20 additional patients enrolling at the Mayo Clinic Rochester site. Patients must have Bipolar I or Bipolar II depression as defined by the Diagnostic and Statistical Manual of Mental Disorders (DSM-5 criteria) and be taking a mood stabilizer acceptable to the principal investigator. They will not be allowed to take antidepressant medication. Their depression must be at least moderate in severity without significant symptoms of activation or mania.

Patients treated may come from the Retreat assisted living, outpatient services, outpatient practices of local psychiatrists, the Sheppard Pratt day hospital, or inpatient units. Patients enrolled at Mayo Clinic will come from their Mood program, Mood Clinic, Inpatient practice and the community. It is unlikely that current inpatients will qualify for this study as most of them will have co-morbidities, psychotic symptoms or mixed presentations which would exclude them.

### **Inclusion and Exclusion Criteria – Phase II**

Patients must meet fulfill all of the following inclusion criteria in order to enter Phase II of the study:

1. Must be at least 18 years old.

2. Must meet **DSM-5** criteria for bipolar (either I or II) depression by clinical interview and M.I.N.I. The duration of the current depressive episode must be at least 4 weeks and no longer than 3 years in length.
3. Should have a MADRS score of at least 20 at screening, an YMRS score of less than 12 and a CGI score of at least 4.
4. Must have signed the informed consent document and have a level of understanding sufficient to provide informed consent and to communicate with the investigator and site personnel.
5. Must be on a mood stabilizer acceptable to the study physician which is consistent with their diagnosis. The mood stabilizer must be at a stable dose for at least four days before starting TMS treatment.
6. If female of childbearing potential, patients must
  - a) have a negative urine pregnancy test at screening, and
  - b) not be nursing or planning a pregnancy, and
  - c) be on a medically acceptable method of birth control acceptable to the principal investigator.

Choices of contraception that meet the study requirements are

- Intrauterine device
- Hormonal contraception (estrogen-containing birth control pills, Vaginal ring, patch, injections or implants)
- Latex condom with spermicide
- Diaphragm with spermicide
- Cervical cap with spermicide

Females of childbearing potential who are abstinent can enroll in the study.

Patients will *not* be enrolled in Phase 2 of the study if they meet any of the following exclusion criteria:

1. May not be directly affiliated with Sheppard Pratt Clinical Research Programs or be immediate family of Research Programs personnel.
2. Must not have another primary Axis I diagnosis.
3. The subject must not have stopped an antidepressant less than two weeks before starting TMS treatment or unable to discontinue antidepressant therapy.
4. Should have no previous history of psychosis or substance dependence or abuse within the six months prior to Screening

5. Presence of an Axis II disorder felt by the investigator to potentially interfere with study compliance would exclude a potential participant.
6. Should not have prior intolerance of TMS or significant lack of response to adequate trials of TMS.
7. Should not have a lifetime history of lack of response to ECT or VNS.
8. Should not have any medical condition likely to interfere with safe study participation.
9. Women of child-bearing potential who are not using a medically accepted means of contraception when engaging in sexual intercourse are excluded, as well as women who are pregnant or breast-feeding.
10. Positive urine screen for any substance of abuse will exclude a patient, with the exception of benzodiazepines. A satisfactory explanation in the opinion of the investigator along with a negative repeat screen prior to Visit 2 is possibly acceptable.
11. Current suicide risk, as evidenced:
  - a) It is the judgment of the investigator that the patient may be at risk for suicide
  - b) The patient has rated a "yes" to question 4 or question 5 on the Screening C-SSRS
  - c) The patient has attempted suicide within the past 12 months prior to Screening.
12. History of head injury, epilepsy or seizure disorder, non-removable metallic implants or objects in or around the head.

### **Inclusion Criteria – Phase III**

Patients who meet MADRS criteria for response or remission will enter Phase III, the six month follow-up phase of the study.

### **Patient Withdrawal**

Patients will be told verbally and in the informed consent that they have the right to withdraw from the study at any time without prejudice or loss of benefits to which they are otherwise entitled.

The investigator may discontinue a patient from the study for the following reasons:

- Non-compliance with 5-day TMS treatment schedule. Patients must complete at least 4 consecutive days of treatment per week.
- It is the judgment of the investigator that the patient may be at risk for suicide
- The patient has rated a “yes” to question 4 or question 5 on the C-SSRS “Since Last Visit” version
- Patient meets relapse criteria (MADRS score  $\geq$  20 for two consecutive weeks
- Onset of manic or mixed symptoms
- Pregnancy
- Intercurrent illness, adverse event or any other reason concerning the well-being of the patient.

Patients who voluntarily withdraw from the study or who are discontinued from the study will be asked to complete an early termination visit. The early termination visit will be done one week after study withdrawal. A MADRS and CGI will be performed by the investigator. Patients will be referred back to their treating psychiatrist for standard clinical care.

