### Phase II: Open Label TMS Treatment

Once study patients are on stable medication and it is confirmed that they meet the entry criteria for Phase II they will begin a standard course of five times a week TMS treatment for six weeks. They will be assessed at each treatment visit for side effects, concomitant medication use, and once per week for severity of depression and evidence of any symptoms suggestive of mania or agitation. Any suggestion of mania or activation will be assessed by the study physician who will evaluate to determine if the subject can remain in the study or needs other intervention to manage emerging symptoms.

The MADRS, the 17-item Hamilton Depression Rating Scale (HAM-D17), the Quick Inventory of Depressive Symptomatology (Self-Report) (QIDS-SR16), the

YMRS, the C-SSRS (Columbia Suicide Severity Rating Scale) and CGI-S will be performed once per week. The CGI-Improvement Scale (CGI-I) will be done weekly starting at Visit 3. Treatment will continue until remission criteria is reached (MADRS score <10) or 30 treatments have occurred, whichever comes first. If improvement is continuing between treatment 25 and 30, treatments may be extended up to 35. Patients who are discontinued due to onset of manic or mixed symptoms will be followed until resolution of these symptoms. Patients who meet response criteria (MADRS score drops by at least 50%) or remission criteria will be followed in Phase III.

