### Treatment Compliance

The goal of treatment is: 1) at least four treatments per week and 2) no more than 3 consecutive days without a treatment. Patients unable to adhere to this schedule will be discontinued.

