### **Statistical Methods**

- Sample Size

We are looking to collect sufficient data to demonstrate the efficacy and safety of TMS in bipolar depression. As this is an open label trial we will aim to treat 30 patients to achieve a reasonable sample size.

- Primary Efficacy Analysis

The primary outcome measure will be the percentage of patients who respond or remit after 30 to 35 treatments. We will subdivide patients based on the diagnosis of either bipolar I or bipolar II to compare effectiveness between those groups.

The other primary outcome will be the percentage of patients who meet criteria for onset of manic symptoms based on the YMRS. The patients will also be separated based on their diagnostic category.

- Secondary Efficacy Analysis

We will also look at the HAM-D and CGI to see the percentage of patients meeting response criteria.

For the patients meeting remission criteria, we will calculate the number of treatments required to achieve remission. Patients who only meet response criteria will be treated for 30 to 35 sessions.

Responders and remitters will also be followed for six months after the final treatment to see the durability of response. Percentage of patients' meeting relapse criteria will be calculated.

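### The two adherence rules disagree: one missed midweek session satisfies Treatment Compliance but can justify removal under Patient Withdrawal

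*Combined protocol and SAP*

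**What the plan says.** The Phase II section sets the schedule: "they will begin a standard course of five times a week TMS treatment for six weeks".

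Two sections then define adequate attendance.

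- **Patient Withdrawal** opens with "The investigator may discontinue a patient from the study for the following reasons". Under non-compliance it states "Patients must complete at least 4 consecutive days of treatment per week".
- **Treatment Compliance** states "The goal of treatment is: 1) at least four treatments per week and 2) no more than 3 consecutive days without a treatment", and then "Patients unable to adhere to this schedule will be discontinued".

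Patient Withdrawal also plans a follow-up rating for anyone who leaves: "The early termination visit will be done one week after study withdrawal. A MADRS and CGI will be performed by the investigator".

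Under Statistical Methods, the primary outcome is the percentage of patients responding or remitting once 30 to 35 treatments have been given. Nothing there says how a patient discontinued earlier is counted, or whether the early termination MADRS contributes. On size, Statistical Methods says "we will aim to treat 30 patients to achieve a reasonable sample size". Study Population expects about 30 patients at the first site, "with 20 additional patients enrolling at the Mayo Clinic Rochester site".

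**The concern.** The two rules apply different tests (a run of consecutive days against a weekly count plus a maximum gap) and carry different consequences (optional against mandatory). No text reconciles them. A patient with good attendance can comply with one section and be removable under the other.

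Treatment is open label and the MADRS is rated weekly, so whoever decides on removal knows both the treatment and the patient's progress. With two sites and no criterion for using the option, practice may differ between them.

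The main efficacy result is a single-arm percentage, so who is removed and who is counted both matter. The denominator is unstated for every withdrawal reason, not only adherence. The gap should not be left to the analyst: the Background section reports the first site's own retrospective response rate (26 of 34, 76.5%) among completers only, so a completer denominator is a familiar convention here.

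**Working it through.** The plan gives no figure to reproduce on this point. The check applies each rule to every relevant attendance pattern.

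**Inputs.** Five sessions a week for six weeks (Phase II section); the two rules as quoted. Assumptions: sessions Monday to Friday, weekends untreated, no make-up sessions, adjacent weeks fully attended unless stated, and any single week or gap outside the limits scored as a breach.

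- Patient Withdrawal is breached if the week has no run of 4 treated weekdays.
- Treatment Compliance is breached if the week has fewer than 4 treatments, or if more than 3 consecutive calendar days pass untreated.

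**One missed session in a week**

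| Missed | Treatments | Longest run | Longest gap (days) | Patient Withdrawal | Treatment Compliance |
|---|---|---|---|---|---|
| Mon | 4 | 4 | 3 | met | met |
| Tue | 4 | 3 | 2 | breached | met |
| Wed | 4 | 2 | 2 | breached | met |
| Thu | 4 | 3 | 2 | breached | met |
| Fri | 4 | 4 | 3 | met | met |

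Over six weeks, 3 × 6 = 18 of 30 session positions breach Patient Withdrawal only. The other 12 breach neither.

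**Two missed sessions in a week.** There are C(5,2) = 10 patterns. Each leaves three treatments, so all breach both rules. Here the tests agree and only the consequence differs.

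**Two successive weeks, at most one miss in each.** There are 6 × 6 = 36 patterns.

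- Neither week has a midweek miss in 3 × 3 = 9. One of these, Friday then the following Monday, leaves a gap of 4 calendar days and breaches Treatment Compliance only. The other 8 breach neither.
- The remaining 36 − 9 = 27 breach Patient Withdrawal only. None breaches both.

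**Calendar or scheduled days.** If only scheduled days counted, four consecutive misses would split 4+0, 3+1 or 2+2 across weeks, so some week would already have at least two misses. The gap limit would add nothing, so calendar days is the more natural reading. On the scheduled-day reading the 36 patterns divide 27 / 0 / 9 / 0 (Patient Withdrawal only / Treatment Compliance only / neither / both), and the midweek result is unchanged.

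These are counts of patterns, not rates; the documents give no missed-session rate.

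**What the denominator could do (illustration; every input below except n is assumed).** Suppose 60% respond, and 1 to 4 removed patients, all with the same outcome, are left out.

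- Non-responders omitted, n = 30: 18/30 = 60.0% becomes 18/29 = 62.1% to 18/26 = 69.2%, or +2.1 to +9.2 points.
- Non-responders omitted, n = 50: 30/50 = 60.0% becomes 30/49 = 61.2% to 30/46 = 65.2%, or +1.2 to +5.2 points.
- Responders omitted: 17/29 to 14/26 (−1.4 to −6.2 points) at n = 30; 29/49 to 26/46 (−0.8 to −3.5) at n = 50.
- Assumed response of 40% to 70%, non-responders omitted: +1.4 (12/29 against 40%) to +10.8 (21/26 against 70%) at n = 30; +0.8 (20/49) to +6.1 (35/46) at n = 50.
- All treated patients counted: no shift from the denominator.

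**The case against.** **The sections can coexist.** Treatment Compliance can be read as mandatory removal and Patient Withdrawal as permitted removal. A reader might infer that the mismatch creates the investigator's discretion. It does not: the discretion comes from the permissive wording of Patient Withdrawal, which also allows removal for any reason bearing on the patient's well-being, and aligning the rules will not remove that. What stands is narrower. Even when the two are reconciled this way, a patient attending four of five sessions remains removable for non-compliance, with no criterion for when to use the option.

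**Treatment Compliance is worded as a goal**, and inability to adhere may mean a continuing problem rather than one bad week. That is fair, and it means scoring every single breach is the strict reading. It does not affect the midweek case, which meets Treatment Compliance on any reading.

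**The counts depend on the calendar.** The plan does not exclude make-up sessions. With a Saturday session, a missed Tuesday still gives four consecutive days, Wednesday to Saturday. The 18 of 30 holds only under the stated schedule.

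**No effect on the result is shown.** A reader might infer that the response rate is biased, or that a completer analysis is intended. The documents support neither. A shift needs removed patients to differ in response and to be left out, and neither is stated. A literal completer reading is also strained, because remitters stop before 30 treatments and must surely count. In addition, the Efficacy Measures section names MADRS change from baseline to endpoint as the primary measure, so the response percentage is not the only claimant to that role.

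**Conclusion.** The inconsistency is real and follows directly from the text. On a Monday-Friday schedule without make-up sessions, one missed Tuesday, Wednesday or Thursday meets Treatment Compliance but breaches Patient Withdrawal. The patient may then be removed at an unblinded investigator's discretion, possibly with different practice at the two sites. A Friday-plus-Monday absence conflicts the other way if calendar days count.

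The number of patients affected is unknown. The effect on the response percentage cannot be computed, may go in either direction, and is zero if all treated patients are counted. The point shifts shown are conditional illustrations, not estimates of bias. This is a drafting fault worth correcting because the repair is cheap; it does not by itself undermine the trial. The missing denominator rule is a wider gap that adherence removals would fall into.

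**What to change.** 1. **Patient Withdrawal.** Delete the word *consecutive* and refer to Treatment Compliance as the single adherence criterion at both sites: at least four treatments per week and no more than 3 consecutive calendar days without treatment. State one consequence, the same in both sections. Add that a single missed session leaving four treatments that week and no gap over 3 days is not a reason for removal. The criterion should not be loosened much further. If removal required breaches in two successive weeks, for example, a patient attending one session in every second week would receive 3 × 5 + 3 × 1 = 18 of 30 treatments and never be removed.

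2. **Statistical Methods.** Count every patient who starts TMS in the denominator of the response/remission percentage. Patients who stop early count as non-responders unless response or remission was met at the last on-treatment MADRS. Patients discontinued for manic or mixed symptoms count as non-responders; otherwise a low MADRS could make a patient who switched an efficacy success, although manic onset is the other primary outcome. Report the early termination MADRS separately.

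**Cost.** Protocol wording only. No extra patients, visits or ratings are needed, since the MADRS is already rated weekly and at early termination. The response figure may be less favourable than a completer figure, and patients with one midweek miss stay in treatment.

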## **Treatment**

Treatment will be done using the Neuronetics NeuroStar TMS Therapy® System. This treatment modality was approved by the Food and Drug Administration for the treatment of Major Depressive Disorder in 2008.

Neuronetics will be providing supplies so there will be no per use charges for patients who are unable to use third party insurance for this study. All subjects at the Sheppard Pratt site will receive TMS treatment at no cost.

### Open Label Treatment with TMS

Stimulation will occur over the left dorsolateral prefrontal cortex at 120% magnetic field intensity relative to the subject’s resting motor threshold, at 10 pulses per second for 4 seconds, with an off time, or intertrain interval, of 26 seconds. Repositioning of the coil, per the NeuroStar User Manual, and prophylactic use of acetaminophen or ibuprofen will be allowed for subjects reporting sensations at or near the stimulation site which are uncomfortable or painful. During the first week of treatment only, in the event that the subject cannot tolerate the treatment at these dose parameters, dose intensity may be titrated downward to 110% of the motor threshold, with all other dose parameters remaining the same. Treatment sessions will last for 37.5 minutes (75 trains) to provide a total of 3,000 pulses per treatment session. All qualified study patients will receive open label TMS treatment, five times a week for a total of 30 treatments or until they meet remission criteria.

### Rationale for Use of Mood Stabilizers

The goal is to make this study as naturalistic as possible. Clinical experience to date is that we have not seen TMS treated bipolar patients becoming manic but there is some risk of activation. Patients with bipolar type I will require mood stabilization within the clear therapeutic range. As there is no clear evidence for what bipolar II patients require for adequate stabilization, the criteria for adequate treatment will be more liberal and patient specific at the discretion of the principal investigator.

### Concomitant Therapy

In general, concomitant medications with primarily central nervous system activity will be kept to a minimum outside of the required mood stabilizing agent. All concomitant medications taken during the study will be recorded on the case report forms. Patients will be instructed to contact the investigator or study coordinator before taking any new prescribed medications, over-the-counter medications or supplements.

Subjects will be allowed to take up to 10 mg of Ambien per night for sleep.

### Treatment Compliance

The goal of treatment is: 1) at least four treatments per week and 2) no more than 3 consecutive days without a treatment. Patients unable to adhere to this schedule will be discontinued.

## **Efficacy Measures and Safety Evaluations**

### Primary Efficacy Measure:

- Montgomery-Asberg Depression Rating Scale (MADRS)

Change from baseline to endpoint in MADRS total score will be the primary efficacy measure. The MADRS is a widely used rating scale for severity of mood related symptoms (Montgomery and Asberg, 1979). The scale consists of 10 items and ranges from 0 to 60. Higher scores denote more severe symptoms. The MADRS score (as opposed to the HAMD) is more sensitive to detect changes in the psychic rather than physical symptoms of depression.

### Secondary Efficacy Measures:

- HAMD-17

The 17-item Hamilton Depression Rating Scale will be used as a secondary rating scale. This scale weights the physical symptoms of depression more than the psychic symptoms (Hamilton, 1960).

- QIDS-SR16

The Quick Inventory of Depressive Symptoms-Self Rating is a 16 item scale in which patients evaluate the severity of their depression. It is able to give an impression from the patients' point of view as to whether or not they are improved and provides a contrast to the clinician-rated scales (Rush 2003).

- C-SSRS

The C-SSRS is a clinician-administered instrument that assesses suicidal ideation (Posner. The "baseline" version of the instrument will be administered at the screening visit. The "since-last-visit" version will be administered at all other visits.

- YMRS

The Young Mania Rating Scale is the most often used scale to assess the degree of manic symptoms a patient has (Young et al., 1978). This scale will be used to screen out patients in mixed or manic states at enrollment and will be used during the trial to assess if the TMS treatment may be inducing mania.

- CGI Severity and CGI Improvement

These are global assessment scales of the severity of a patient's illness on a seven-point scale and degree of change from baseline on a seven-point scale (Guy, 1976). The CGI improvement scale is often the most sensitive marker to recognize status change in patients.

### **Safety Evaluations**

The investigator or his designee is responsible for the medical care of study patients during the study. The investigator remains responsible for following, through an appropriate health care option, adverse events that are serious or that caused the patient to discontinue before completing the study. The patient will be followed until the event is resolved or explained.

### **Adverse Events**

Prior to enrollment, study site personnel will note the occurrence and nature of each patient's medical condition(s). During the study, site personnel will again note any change in the existing conditions and the occurrence and nature of any new adverse events.

If a patient experiences an adverse event after the informed consent is signed, but before study drug is given, the event will be noted as a pre-existing condition unless the investigator believes that the event may have been caused by a protocol procedure.

The Data Safety Management Board (DSMB) and the IRB for this study will evaluate all adverse event reports including data from both sites.

